12.2.1 Assessment of Intensity

An assessment of intensity grade will be made using the general categorical descriptors outlined in the WHO Toxicity Grading Scale (see Table below). The investigator should use clinical judgment in assessing the severity of events not directly experienced by the subject (e. g, laboratory abnormalities).

MILD	Does not interfere with subject's usual function, easily tolerated.
MODERATE	Interferes to some extent with subject's usual function.
SEVERE	Interferes significantly with subject's usual function, incapacitating with inability to work or carry out usual activity.

12.2.2 Assessment of Seriousness (AE vs. SAE)

Determination of the seriousness of the adverse event according to the definitions for a serious adverse event (SAE) given in section 12.1.

12.2.3 Assessment of Causality

Determination of the relationship of the adverse events to the medicinal product(s) being studied after having evaluated all accessible data according to the following classification:

Suspected relationship (related):

The temporal relationship between the event and the administration of the IMP makes a **causal relationship possible, probable, or definite**, or other drugs, therapeutic interventions or underlying conditions do not provide a sufficient explanation for the observed event.

No suspected relationship (not related):

The temporal relationship between the event and the administration of the IMP makes a **causal relationship unlikely or impossible (i.e. not related)**, or other drugs, therapeutic interventions or underlying conditions provide a sufficient explanation for the observed event.

The evaluation should consider nature and pattern of the reaction, temporal relationship to study medication, the clinical status of the patient, the concomitant medication and other relevant parameters. When the final causality assessment is unknown and it is uncertain whether or not the investigational product caused the event, then the event should be handled as an SAE related (suspected) to the investigational product for reporting purposes. If the investigator believes that the SAE is not related to the investigational product but is potentially related to the conditions of the trial the relationship should be specified in the narrative section of the SAE report form.

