8.2 Treatment Groups

Treatment A: Nicotinell 14mg/24h patch

Treatment B: Placebo patch

Treatment A or Treatment B will be applied for 7 consecutive days (Day 1 to Day 7) once daily.

Patients will be treated with either Treatment A or Treatment B according to the randomization list.

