10.8 Dosage, Mode of Application and Dose Schedule of IMP

IMP patches will be applied by unblinded members of the investigator's team only.

Application on Day 1 will be done during or immediately after surgery. Application on Days 2 to 7 should be done preferably in the morning with an interval of approximately 24h (+/-6h) between treatments.

The dose of 14mg/24h for Nicotine patches was chosen as the medium dose for Nicotine patches being used for smoking cessation. This dose was proven safe even in non-smokers with only transient nausea as the only symptom [55] and in the elderly, where no serious adverse events were noted [63]. Also in critically-ill patients, a dosing of 14mg/24h was tolerated without relevant side-effects [61]. The dose was chosen to have most likely a significant effect without causing harm to the subjects.

According to the SmPC, the patch has to be placed either on the upper arm, upper hip or in the shoulder area. For standardization purposes in this study, the patches will be applied on the upper arm.

The patch should be placed on non-injured, clean and dry skin with as less hair as possible. The patch will be left on the application area for approximately 24 hours (+/-6h) after which the patch will be replaced by a new one. The application area has to be changed every day to avoid skin reactions. Therefore, it is preferred to change the arm for application every day.

After application of the Verum or Placebo patch, another patch has to be placed over the IMP patch to cover it for blinding purposes. This "blinding patch" has to cover the IMP patch totally. It has to be ensured that any manipulation of the "blinding patch" can be discovered.

Both patches (the IMP patch and the "blinding patch") must not be taken off during the time of application e.g. for taking a shower. Although the IMP patch is not water-resistant, it can be left on the skin when showering carefully.

The application and blinding process is described in detail in the IMP Manual.

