12.5 Documentation and Reporting of SAEs

Every SAE will always be documented in the patient file and in the eCRF even if they are

- not severe
- meeting CTCAE grade 1 or 2
- not at least possibly related
- declared in the protocol as being exempt from reporting without undue delay, by the investigator to sponsor (refer to Section 12.5.1)
- primarily attributed to the underlying disease

Every SAE has to be reported immediately to the Sponsor Delegated Person/ Coordinating Investigator and SZB except those SAEs the protocol identifies as not requiring immediate reporting. However, **every SAE that is considered related to the IMP will always be reported to the Sponsor Delegated Person/ Coordinating Investigator without undue delay** According to the documentation of AEs any adverse event in patients of

the control arm meeting the criteria of an SAE will also be recorded although no study drug will be administered to ensure comparability of the safety data of the two study arms.

The documentation of the SAEs for a patient is carried out as described under 12.4, the reporting of SAEs for study patients is carried out within the following time periods:

- after the subject has been randomized and has received IMP for the first time
- up to 24h after the subject has received the last dose of IMP
- after these time periods until end of trial, when the SAE is believed to be related to the IMP
- after the end of trial when the investigator becomes aware of a SAE with a suspected causal relationship to the IMP

Any SAE occurred after application of study drug should be reported **immediately** after investigator awareness of the event to the sponsor (at the latest within 24 hours):

Study Coordinating Center of the SZB
Studienzentrale Studienzentrums Bonn (SZB)
[contact]
E-Mail: [contact]

Reporting should occur by fax on the **SAE report form** provided for this purpose. Symptoms, signs and laboratory changes should, as far as possible, be combined into one **single diagnosis**. The investigator is responsible for assessing the event (seriousness, intensity, causality). If necessary information is not fully available at this time, follow-up reports should be sent as soon as possible. Questions must be answered promptly. Further information and details how to report are described in the **Safety Management Plan**.

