12.5.1 Serious Adverse Events exempted from expedited reporting

According to the ICH Guideline E19² in certain situations selective safety reporting may be appropriate. This applies for example if the IMP has received a marketing authorization from a regulatory authority, the safety profile is well-known, the clinical pharmacology has been described and understood, post-authorization data is sufficiently available.

In this clinical trial the test-IMP has a marketing authorization for more than 30 years in Germany and a very well-know safety profile from a large number of post-authorization data [54]. The aim of this trial is to provide evidence of efficacy of nicotine treatment in patients suffering from DGE after PD.

Surgical resection is a pre-planned procedure and not considered as trial treatment. Therefore, complications from surgical resection (PD) from the date of surgery until the end of follow-up are not considered AEs/SAEs unless the complications are considered to be related to treatment with the IMP. Surgical complications will be documented in the eCRF and the patient file.

Furthermore, events that are probably related to the underlying disease are not considered as AE/SAE as long as the severity of the event is to be expected and not aggravated.

² ICH Guideline E19 on a selective approach to safety data collection in specific late-stage pre-approval or post-approval clinical trials (16-Mar-2023)

The underlying disease is a condition prior to inclusion in the clinical trial. Events that are probably related to the underlying disease are not considered as AE/SAE as long as the event and the severity of the event are to be expected and not aggravated.

The following events are most likely to occur after surgical resection or are most likely related to the underlying disease:

- Postoperative pancreatic fistula
- Relaparotomy
- Postoperative haemorrhage
- Insufficiency of the biliodigestive anastomosis
- Insufficiency of the GE (Gastroenterostomy)
- (Superficial) wound infections
- Intra-abdominal abscess
- Pleural effusion
- Pneumonia

In recent studies, nicotine application was extremely safe in terms of anastomotic healing and surgical site infections [59,60]

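### The 'related' and 'not related' causality definitions in 12.2.3 both join their tests with 'or', so two of the four possible combinations fall in both classes

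*Protocol*

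**What the plan says.** Section 12.2.3 gives two classes, each built from two tests.

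- **Related:** the timing makes a causal link at least possible, "or other drugs, therapeutic interventions or underlying conditions do not provide a sufficient explanation for the observed event".
- **Not related:** the timing makes a causal link unlikely or rules it out, "or other drugs, therapeutic interventions or underlying conditions provide a sufficient explanation for the observed event".

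The section then lists what to weigh: "The evaluation should consider nature and pattern of the reaction, temporal relationship to study medication, the clinical status of the patient", together with concomitant medication and other relevant parameters. If the final assessment is unknown and it is uncertain whether the product caused the event, "then the event should be handled as an SAE related (suspected) to the investigational product for reporting purposes".

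Other sections use the resulting label:

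- 12.5.1: complications of the resection "are not considered AEs/SAEs unless the complications are considered to be related to treatment with the IMP".
- 12.5: some SAEs are exempt from immediate reporting, but "every SAE that is considered related to the IMP will always be reported to the Sponsor Delegated Person" without undue delay. Later than 24 hours after the last dose, an SAE is reportable only if believed related.
- 12.1.5: a SUSAR must first be a suspected reaction.

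On exposure, 10.8 states "Application on Day 1 will be done during or immediately after surgery", and 8.2 states "Treatment A or Treatment B will be applied for 7 consecutive days (Day 1 to Day 7) once daily".

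**The concern.** A two-class rule should put each event in one class. Here the second test of each definition is the negation of the other's, and so is the first. Joining both pairs with *or* makes the definitions overlap.

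Patch treatment coincides with the first post-operative week. An investigator will often judge a link to the patch possible and also regard the operation as a sufficient explanation. That event meets both definitions. Two of the roughly six sites could then label the same kind of complication differently, each following the text. At stake are the AE/SAE status of surgical complications, the reporting of exempted and late SAEs, SUSAR status, and the meaning of any table of related events.

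**Working it through.** No sample size or error rate is involved, and the plan gives no figure to reproduce. The check is to enumerate the rule.

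**Inputs (all from 12.2.3).** Let L mean that the investigator judges a causal link at least possible. Let E mean that another sufficient explanation exists.

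- Related = L or (not E)
- Not related = (not L) or E

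**As written:**

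| L: link possible | E: other explanation | Related | Not related | Result |
|---|---|---|---|---|
| yes | yes | met | met | both classes |
| yes | no | met | not met | related only |
| no | yes | not met | met | not related only |
| no | no | met | met | both classes |

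Two of four combinations are classified cleanly and two fall in both classes. No combination falls in neither.

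**Is there a rule of precedence?**

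- The factors to weigh in 12.2.3 have no stated order and do not say which definition wins.
- The uncertainty sentence requires an assessment that is unknown and uncertain. It is worded for SAEs and for reporting. An investigator who is confident that the operation suffices does not reach it.
- The list in 12.5.1 names events most likely due to surgery or the underlying disease. It does not say that they are unrelated whenever a link to the patch is possible.
- The sponsor's second assessment in 12.3 covers SAEs. Under 12.5.1 a surgical complication judged unrelated is not an SAE, so it may never reach that step.
- 12.1.2 counts an event as a reaction if a causal link cannot be excluded. This conflicts with the branch of 12.2.3 that makes an event unrelated merely because another explanation suffices.

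**After changing the joining word to *and* in the not-related definition:** not related = (not L) and E. This is exactly the negation of L or (not E).

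| L | E | Related | Not related |
|---|---|---|---|
| yes | yes | met | not met |
| yes | no | met | not met |
| no | yes | not met | met |
| no | no | met | not met |

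All four combinations now have one class. Both formerly ambiguous ones become related, in line with 12.1.2.

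**The case against.** **The first test is a causal judgement, not a calendar check.** A reader might infer that every SAE under the patch is automatically related because the timing fits. The text does not say this. Section 12.2.3 asks for a judgement on all accessible data, and an investigator may call a link unlikely on Day 5 with the patch in place. This stands. It reduces how often the overlap arises but does not remove it where a link is judged possible and surgery also suffices.

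**The protocol gives some direction.** The list in 12.5.1 points typical complications towards surgery, the uncertainty sentence points doubtful SAEs towards related, and 12.3 says the sponsor should not downgrade the investigator's causality assessment. A Safety Management Plan, not at hand, holds further detail. These are partial aids. They pull in different directions, and none changes the two definitions.

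**Consequences are limited.** A reader might infer that a false safety signal could be manufactured. The documents do not support that. Surgical complications are still entered in the eCRF (12.5.1). Fistula, haemorrhage, fluid collections, surgical site infection, re-operation, mortality and cardiovascular events are secondary endpoints summarised by treatment (14.2.2, 14.2.5). The DSMB reviews safety data in both arms (section 13). Investigators are blinded (10.12) and the 1:1 randomisation is stratified by site (9.6), so differing site habits should fall about equally on both arms and mainly add noise. Every SAE is documented whatever its causality, and up to 24 hours after the last dose non-exempt SAEs are reported regardless of it (12.5). All this stands and confines the problem to the uses of the label itself.

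**Conclusion.** The two definitions are not complements as worded: two of four combinations meet both, and nothing in the protocol sets precedence. This is an error in a rule that the protocol itself fixes, not a detail left to another document.

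The effect is on the AE/SAE status of surgical complications, the reporting of exempted and late SAEs, SUSAR status, and counts of related events. Complication totals by arm and the primary analysis of delayed gastric emptying do not use the label.

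That the first overlapping combination will be common rests on the coincidence of patch treatment with the early post-operative period. The protocol gives no figure for the share of events, and none is claimed. Nor does the rule fail altogether, as a reader might infer: the other two combinations are classified cleanly.

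**What to change.** In the not-related definition of 12.2.3, change the *or* between the timing test and the other-explanation test to *and*; the *or* inside the list of other explanations stays. An event is then not related only if a causal link is unlikely or ruled out and another sufficient explanation exists. Leave the related definition and the uncertainty sentence unchanged.

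Putting *and* into the related definition would also remove the overlap. But it would make an event unrelated whenever surgery suffices, even with a possible link to the patch, which conflicts with 12.1.2.

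Reconcile 12.1.2, 12.2.3 and 12.5.1 in the same step, so that the exemption for surgical complications rests on the corrected classes. Use identical text in the Safety Management Plan and the SAE form.

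**Cost:** one word plus matching text in two documents. Somewhat more events will be classed as related and reported, chiefly complications for which a link to the patch is judged possible although surgery also explains them.

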12.3 Criteria to be evaluated by the Sponsor for SAEs (2nd assessment)

To take into account safety data available to the sponsor but not to the investigator at the time an SAE was detected, in addition to the initial assessment of a serious adverse event by the investigator, a second assessment of the event by the sponsor in terms of causality and probability of occurrence ("expectedness") and a continuous benefit-risk assessment are performed.

- **Causality:** If no information on causality is available from the investigator rapporteur, the sponsor should consult the investigator rapporteur and ask him to comment on this aspect. The sponsor should not downgrade the investigator's assessment of causality. If the sponsor disagrees with the investigator on the causal link, the report should include the opinion of both the investigator and the sponsor.
- **Expectedness:** Whether a serious adverse reaction is to be expected is assessed using the reference safety information (RSI). If the rapporteur investigator has provided information on whether an event is expected, the sponsor should take this into account.

12.4 Documentation and Reporting of AEs, Follow-up

Any AE defined in clinical trial protocol as relevant for the evaluation and analysis of the clinical trial has to be documented in the CRF on the respective Adverse Event Report Form. Documentation and evaluation of each AE occurring between:

- the visit with the first administration of IMP to the subject and
- the visit of discharge.

According to the CTR, only adverse events and unexpected clinical diagnostic findings that are identified in the protocol as critical to safety evaluations must be reported by the investigator to the sponsor.

All medical conditions prevalent prior to study enrolment and all Adverse Events (AE) that occur after first dosing until discharge will be collected throughout the study and documented in the subject's medical record using medical terminology and transferred to the CRF. If applicable, AEs and SAEs that relate to any later protocol-specified procedure will be recorded. Furthermore, the investigator should report any SAE that occurs after these time periods and after end of the clinical trial, if the SAE is believed to be related to the study drug. An SAE report should be completed for any event where doubt exists regarding its seriousness. To ensure comparability of the safety data of the two study arms any adverse event in patients of the control arm will also be recorded although no study drug will be administered. Whenever possible, diagnoses should be given when signs and symptoms are due to a common etiology. All measures required for adverse event management must be recorded in the source document and reported according to sponsor's instructions. The investigator evaluates all Adverse Events regarding severity, causality as well as seriousness.

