Attachment 001 to SOP MW-009.001

Version 001

Page 12 of 69

Clinical Trial Protocol version 2.0 28-JUN-2023

Effective Date: 18-Mai-2022

	
 8. Known history of hypersensitivity to nicotine or a component of the investigational drug 9. Systemic skin diseases (e.g. Lupus erythematoses) 10. Immediately after heart attack 11. Severe cardiac arrhythmia 12. Stroke that occurred shortly before 13. Concomitant medication with inhibitors or strong inducers of CYP2A6 (e.g. Trancylpromine, Desipramin, Ketoconazole, Valproic acid, Pheno-barbital, Pilocarpine, Clotrimazole, Methoxsalen, Rifampicin)
Trial Procedures	
Screening-Visit (Day -28 to Day -1)
 
Visit 1 (Day 1, Surgery)
 
Visit 1.2 – 1.7 (Post-operative Day 2 to Day 7)
 
Visit 2 (Post-operative Day 14)
 
Visit 3 (Post-operative Day 21 or discharge – whatever comes first)
 
Visit 4 (Post-operative Day 30, follow Up)

Trial Specific Measurements	
 • Application of IMP-/Placebo-patch • Assessment of primary and secondary endpoints
Investigational trial sites	
This is a multi-center trial with about six (6) investigational trial sites in Germany.

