Attachment 001 to SOP MW-009.001

Version 001

Page 15 of 69

Clinical Trial Protocol version 2.0 of 28-JUN-2023

Effective Date: 18-Mai-2022

	Screening Visit	Treatment Phase		Follow up Phase		End of Trial
Time points (accepted deviation)	Day -28 to Day -1	Day 1 (Surgery)	Day 2 to Day 7	Day 14 (+/- 1 Day)	Day 21 (+/-1 Day) or Discharge	Day 30 (+/- 2 Days)
Visit No.	0	1	1.2 to 1.7	2	3	4
QLQ-C30						√
PAN26						√

¹ according to the definition of the International Study Group of Pancreatic Surgery. NGT requirement + solid food intake on every visit day indicated, all other parameters only on Visit 1.3, 1.7, 2 and 3.

² especially: surgical site infections, cardiovascular events, mortality

³ Visit 1 only Lymphadenectomy, re-intervention, re-operation, nausea, cardiovascular events. Visit 1.2, 1.3, 1.5-1.7 no assessment. Visit 1.4, 2, 3, 4 only pancreatic fistula, postoperative hemorrhage, intra-abdominal fluid collections, re-laparotomy

⁴ Exclusion Criterion No. 5 can only be answered during surgery

3 Abbreviations

AR	Adverse (Drug) Reaction
AE	Adverse Event
AMG	Arzneimittelgesetz
CA	Competent Authority
CI	Coordinating Investigator
CRA	Clinical Research Associate
CRF	Case Report Form
CRO	Contract Research Organization
CTR	Clinical Trial Regulation
DGE	Delayed Gastric Emptying
EC	Ethics Committee
FPFV	First Patient First Visit
FPI	First Patient In
GCP	Good Clinical Practice
GDPR	General Data Protection Regulation
ICH	International Conference on Harmonization
IMP	Investigational Medicinal Product
ISF	Trial site File
LPLV	Last Patient Last Visit
LPO	Last Patient Out
NGT	Naso-gastric tube
PD	Pancreatoduodenectomy
PI	Principal Investigator
SAR	Serious Adverse Reaction
SAE	Serious Adverse Event
SDP	Sponsor Delegated Person
SUSAR	Suspected Unexpected Serious Adverse Reaction
SZB	Study Center Bonn (Studienzentrum Bonn)
UAR	Unexpected Adverse Reaction

4 Trial Administration structure

Coordinating Investigator and Sponsor Delegated Person	[name] Department of Surgery University Hospital Bonn [name] [contact] Email: [contact]
Sponsor	Medical Faculty of the University of Bonn, represented by the Dean [name]
Coordinating institution	Clinical Study Core Unit, Study Center Bonn (SZB) Institute for clinical chemistry and clinical pharmacology University Hospital Bonn [name]
Participating trial site(s)	6 German sites are planned

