The most frequent complication following pancreatoduodenectomy (PD) is delayed gastric emptying (DGE) with a reported incidence of 19%-57% [1]. A wide range of causative mechanisms has been proposed for DGE: the absence of hormonal stimulation due to the resection of the duodenum, ischemia of the stomach and duodenum following resection, denervation of the stomach and duodenum, post-operative pylorospasm, DGE secondary to other intraabdominal complications, pancreatic fibrosis, cholangitis, pancreatitis, alteration of the endocrinologic milieu or torsion/angulation of the reconstructed alimentary tract [2]. In fact, most studies concentrating on DGE accused technical aspects of the reconstruction to cause DGE, but none was able to ameliorate DGE. Neither ante- or retrocolic reconstruction route [3], pylorus resection and –preservation [4], nor single versus double loop reconstruction [5] does influence the frequency of DGE following PD. Often, DGE is self-limiting [2] and does not increase periprocedural mortality [6,7], but DGE is known to significantly increase hospital stay [8]. Recently DGE was described for the first time to negatively affect cancer specific survival [9]. So, strategies are needed for the treatment of delayed gastric emptying to increase the utilization of adjuvant chemotherapy with the goal of improved overall survival.

The aim of this clinical trial is to assess the effect of transcutaneous administered nicotine on the development and severity of delayed gastric emptying (DGE) following pancreatoduodenectomy (PD) as compared to placebo.

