6.1 Benefit for study participants and patient population

With the application of a transdermal nicotine patch the respective patient population has the change to benefit from a lower incidence of DGE following PD. As a result, these patients may recover earlier, in connection with a perspective of a shorter hospital stay and improved quality of life, and, hopefully, will show an increased utilization of adjuvant treatment.

Patients receiving the placebo patch do not have an additional therapeutic benefit beyond the one conveyed by standard therapy regularly applied.

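### Section 12.4 stops adverse event documentation at discharge while the schedule runs it to Day 30, and the discharge cutoff ties observation time to length of stay, which treatment may change

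*Protocol*

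**What the plan says.** Section 12.4 sets the documentation window twice. A bulleted definition runs from the visit with the first patch to "the visit of discharge". The text below it repeats that "all Adverse Events (AE) that occur after first dosing until discharge will be collected throughout the study". After discharge, 12.4 keeps only events tied to a later protocol procedure and SAEs believed related to the study drug.

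Section 12.5 says SAEs are documented as in 12.4. It then gives separate periods for reporting them: "up to 24h after the subject has received the last dose of IMP", and after that only if believed related to the IMP.

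The schedule in section 2 ticks the AE/SAE row at Day 1, Days 2 to 7, Day 14, Day 21 or discharge, and Day 30. Only screening is blank. Its footnote 2 reads "especially: surgical site infections, cardiovascular events, mortality". According to the synopsis, Visit 3 falls on Day 21 or at discharge, whichever is earlier, and Visit 4 is a separate follow-up on Day 30.

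On length of stay, the Introduction says "DGE is known to significantly increase hospital stay". Section 6.1 describes the hoped-for benefit of nicotine "in connection with a perspective of a shorter hospital stay and improved quality of life". Section 14.2.5 summarises safety descriptively, or by absolute and relative frequencies, by treatment.

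**The concern.** There are two problems. First, the documents give two different ends for AE and SAE documentation. A site following 12.4 stops at discharge and a site following the schedule goes on to Day 30. Both comply, yet they collect different data.

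Second, if 12.4 governs, the observation window is itself a post-randomisation outcome. Length of stay lies downstream of the condition that nicotine is meant to prevent. If nicotine shortens stay, its arm is watched for less time, and unadjusted frequencies will tend to show fewer events on nicotine even when the underlying risk is the same. That works against the aim, stated in 12.4 itself, of keeping safety data comparable between the arms.

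**Working it through.** **1. The passages side by side**

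| Text | What it governs | End of window |
|---|---|---|
| 12.4 (stated twice) | AE documentation | Discharge |
| 12.5, cross-reference to 12.4 | SAE documentation | Discharge |
| Section 2, AE/SAE row | AEs and SAEs | Visit 4, Day 30 |
| 12.5, reporting periods | SAE reporting to the sponsor | 24 h after last dose, then related SAEs only |

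The first two rows conflict with the third. The fourth concerns reporting, a separate matter. Section 12.5 also asks that every SAE be documented even if unrelated, but that sentence sets no period. The period comes from the cross-reference to 12.4.

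**2. Share of the 30-day window observed under 12.4**

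Discharge on Day 10: 10/30 = 33%. Day 14: 14/30 = 47%. Day 21: 21/30 = 70%.

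**3. Possible size**

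The protocol states no figure to reproduce, and it gives neither length of stay nor AE rates. The following are assumptions: mean placebo stay 14, 18 or 21 days; nicotine stay 1, 2 or 4 days shorter; the same constant daily hazard in both arms.

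Ratio of expected recorded AE counts = (nicotine stay)/(placebo stay):

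| Placebo stay | 1 day shorter | 2 days shorter | 4 days shorter |
|---|---|---|---|
| 14 | 13/14 = 0.93 | 12/14 = 0.86 | 10/14 = 0.71 |
| 18 | 17/18 = 0.94 | 16/18 = 0.89 | 14/18 = 0.78 |
| 21 | 20/21 = 0.95 | 19/21 = 0.90 | 17/21 = 0.81 |

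For the share of patients with an AE, let R be the 30-day risk (assumed 20% or 40%), h = −ln(1 − R)/30, and recorded risk by discharge day L = 1 − exp(−hL). With R = 20%, h = 0.2231/30 = 0.00744. Stays of 14 and 10 days then give 9.9% and 7.2%, a spurious difference of −2.7 points. Over the whole grid the difference is −0.6 to −2.7 points at R = 20%, and −1.2 to −5.6 points at R = 40%. All of these favour nicotine.

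**4. Bounds on this illustration**

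Patches are worn on Days 1 to 7, and every stay in the grid (10 to 21 days) covers that period. If all events fell within those 7 days, both arms would be fully observed and the ratio would be 1. Real data would lie between that and the constant-hazard figures.

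A 4-day difference also looks large. Section 5.2 reports DGE in 40% of smokers and 53% of non- or former smokers, a gap of 13 points. If stay shortened only through averted DGE, a mean reduction of 1 day would need 1/0.13 ≈ 8 extra days per averted case, 2 days would need 2/0.13 ≈ 15, and 4 days would need 4/0.13 ≈ 31. Less severe DGE among those who still develop it would lower these figures.

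**5. With a fixed window to Day 30**

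Under equal hazards, every surviving patient who has not withdrawn has the same window. The expected ratio is 1.00 and the difference 0, whatever the stay.

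**The case against.** The strongest reply is that little of importance depends on the 12.4 window. Much of this stands:

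- A reader might infer that 12.4, the schedule and 12.5 give three mutually contradictory windows. They do not. Section 12.5 separates documentation from reporting, and a shorter reporting period is no contradiction.
- A reader might infer that post-discharge infections and other complications are lost. Section 12.5.1 treats surgical complications up to the end of follow-up as outside the AE/SAE route unless IMP-related, and has them documented in the eCRF. Its list includes wound infection, abscess and pneumonia. Footnote 3 to the schedule has fistula, haemorrhage, fluid collections and re-laparotomy checked at Visit 4.
- Mortality enters MTL30, which is ticked at Day 30.
- SAEs believed related to the IMP stay reportable after discharge, and 12.2.3 treats uncertain causality as related.
- A reader might infer that cardiovascular events are restricted to the admission. In the endpoint wording that restriction may apply only to revascularisation.
- Days of postoperative stay are recorded, so exposure-adjusted rates are possible, and the SAP is not shown.
- If the discharge visit means Visit 3, long stays are capped at Day 21 in both arms, which reduces any imbalance.

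Three things remain. The conflict between 12.4 and the schedule is not resolved anywhere in the protocol. Adjusting for exposure does not recover events that were never documented. And the separate cardiovascular check is listed in footnote 3 only at Visit 1, so later cardiovascular events depend on the AE/SAE route that 12.4 closes at discharge.

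**Conclusion.** The point holds in limited form. Section 12.4, with the SAE documentation tied to it, contradicts the schedule, and its discharge cutoff makes observation time depend on an outcome that treatment may affect. The direction, towards nicotine, is conditional on nicotine actually shortening stay. A reader might take the safety comparison to be biased as a matter of fact, or by a known percentage; the documents support neither. The count ratios of 0.95 to 0.71 rest on assumed stays and a constant hazard, and would be less extreme if events cluster during treatment. What is exposed is mainly non-serious AEs after discharge and post-discharge SAEs judged unrelated, including cardiovascular events. The matter should be settled because the correction is cheap and the schedule already provides for it.

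**What to change.** Reconcile 12.4, and the sentence in 12.5 that refers SAE documentation to it, with the schedule. One window should apply: AEs and SAEs are documented for analysis from the first patch to Visit 4 (Day 30) in every treated patient, regardless of the date of discharge and of judged causality. The SAE reporting timelines in 12.5 and the exemptions in 12.5.1 can stay as they are.

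The cost is a wording change and slightly more AE entry. Visit 4 and its AE tick already exist, so no visit is added.
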